Original Cohort: The *primary study endpoint* is complete response (CR) rate at the time of AHCT and is based on the Lugano Criteria.¹⁶ The primary endpoint for the patient *safety monitoring* segment of the study is toxicity. Toxicity will be scored using the NCI CTCAE v4.03 Scale. Unacceptable toxicity in a given patient is defined as any non-hematologic or hematological grade 3/4 toxicity that does not resolve to a grade 1/2 within 14 days per NCI CTCAE v4.03 toxicity criteria and is considered at least possibly related to nivolumab and/or ICE, or any other regimen-related cause of death.

New Cohort (B): The first primary endpoint is unacceptable toxicity. Toxicity will be scored using the NCI CTCAE v4.03 Scale. Unacceptable toxicity in a given patient is defined as any non-hematologic or hematological grade 3/4 toxicity that does not resolve to a grade 1/2 within 14 days per NCI CTCAE v4.03 toxicity criteria and is considered at least possibly related to nivolumab and/or ICE, or any other regimen-related cause of death. **Updated Apr 27, 2021:** The phase 2 portion will evaluate the anti-lymphoma activity of the two-agent combination as assessed by CR rate using Lugano criteria, in patients with high-risk HL as the second primary endpoint.

Sample Size:

Original Cohort (A): Assuming 1) the nivolumab 240 mg flat dose and ICE doses are well tolerated and 2) the study does not close for futility, 43 evaluable (received at least one cycle of treatment) patients will be enrolled on the phase II portion of the study. Expected accrual for safety monitoring segment: n=6.

New Cohort (B): We plan to enroll and treat 18 eligible patients. With 18 patients, we can estimate the proportion of patients experiencing unacceptable adverse events with sufficient precision (standard error ≤ 0.12 , half width ≤ 0.23). **Expanded Sample Size (Anti-Lymphoma Activity):** The Cohort B phase 2

portion is expected to enroll and treat a minimum of 19 and a maximum of 35 patients at the Cohort B schedule.

Estimated Duration of the Study

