7.2 Dose Delay Criteria for NIVO + ICE

Dose delays for NIVO + ICE are allowed under the following criteria:

- Hematological toxicity: Platelets $\leq 75,000$, Hemoglobin ≤ 8.5 , ANC $\leq 1,500$
- Non-hematological toxicity: All drug-related grade 3/4 AEs. These AEs need to resolve to grade 2 or lower before NIVO + ICE is given.

A delay of up to 14 days is allowed. After 14 days of delay, patients must be taken off the trial.

Filgrastim/packed red blood cells/platelet transfusions are allowed during this period, even during DLT assessment, as ICE therapy itself is supported by these transfusions.

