11.1 Definitions

Evaluable for toxicity: All participants will be evaluable for toxicity from the time of their first treatment with nivolumab.

Evaluable for objective response: Only those participants who have measurable disease present at baseline, have received at least 4 weeks of therapy, and have had their disease re-evaluated will be considered evaluable for response. These participants will have their response classified according to the definitions stated below.

Duration of overall response: The duration of overall response is measured from the time measurement criteria are met for CR or PR, per 2014 Lugano Criteria,¹⁶ (whichever is first recorded) until the first date that relapsed or progressive disease is objectively documented.

Duration of overall CR: The duration of overall CR is measured from the time measurement criteria are first met for CR until the first date that progressive disease is objectively documented.

Duration of stable disease: Stable disease is measured from the start of the treatment until the criteria for progression are met, per 2014 Lugano Criteria,¹⁶ taking as reference the smallest measurements recorded since the treatment started, including the baseline measurements.

Overall Survival (OS): OS is defined as the duration of time from start of treatment to time of death (due to any cause).

Progression-Free Survival (PFS): PFS is defined as the duration of time from start of treatment to time of progression or death, whichever occurs first.

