Study Design Characteristics: This phase II trial will implement a Simon Two-Stage Optimal Design¹⁵ to evaluate the anti-lymphoma activity of NIVO± ICE chemotherapy. The trial is expected to enroll a minimum of 15 and a maximum of 43 subjects. The sample size is based on the desire to discriminate a promising CR rate of 70% from a disappointing CR rate of 50% (a rate below what can be achieved with ICE/augmented ICE) using a type I error rate of 0.05 and power of 80%. At stage 1, 15 subjects will be entered on the study. If ≤ 8 complete responses are seen, the study will be terminated. If at least 9 subjects achieve a CR, the trial will continue to the second stage. At stage 2, 28 additional subjects will be entered. At the end of stage 2, if 27 or more subjects experience a complete response, the combination will be considered worthy of further study. If ≤ 26 subjects experience a complete response then no further investigation of the regimen is warranted.

Safety Monitoring Segment: NIVO is already FDA approved for treatment of HL and thus does not require special safety monitoring. Since the combination of nivolumab and ICE has not been tested before, the trial will include a 6-patient safety monitoring cohort for patients treated with nivolumab plus ICE (cycle 1). If $\leq 1/6$ patients experience unacceptable toxicity, then the study will continue. If 2 or more patients experience unacceptable toxicity, we will stagger the dose of nivolumab and ICE by 1 week so that nivolumab will start on day 1 and ICE will start on day 8 of a 21 day cycle. There will then be another 6 patient cohort added to the monitoring. If $\leq 1/6$ patients experience unacceptable toxicity in the staggered cohort, then the study will continue. If, however, 2 or more patients experience unacceptable toxicity in the staggered cohort, then nivolumab will not be given in combination with ICE.

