The phase 2 portion will implement a Simon two-stage minimax design^{15,87} to evaluate the anti-lymphoma activity of the two-agent combination as assessed by CR rate, in patients with high-risk HL. The Cohort B phase 2 portion is expected to enroll and treat a minimum of 19 and a maximum of 35 patients at the Cohort B schedule. The sample size is based on the desire to discriminate a promising CR rate of 74% from a disappointing response rate of 50%³ using a type I error rate of 0.05 and power of 90%. At stage 1, 19 patients will be entered on the study. Note: The n=13 patients treated thus far as part of the safety evaluation portion of the study will count toward the 35 patients required; given this, we expect to enroll only 22 new patients on the Cohort B phase 2 trial. If ≤ 9 complete responses are seen, the study will be terminated. If at least 10 patients achieve CR, the trial will continue to the second stage. At stage 2, 16 additional patients will be entered. At the end of stage 2, if 23 or more patients experience complete response, the combination will be considered worthy of further study. If ≤ 22 patients achieve a complete response then no further investigation of the combination is warranted.

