12.2 Sample Size Accrual Rate

Assuming 1) nivolumab and NIVO + ICE are well tolerated and 2) the study does not close for futility, 43 evaluable patients will be enrolled on the phase II portion of the study. Study enrollment will be complete within 24 months from activation (accrual of 1-2 participants per month). Expected accrual for the safety monitoring segment: n=6.

Sample Size, Cohort B: We plan to enroll and treat 18 eligible patients. With 18 patients, we can estimate the proportion of patients experiencing unacceptable adverse events with sufficient precision (standard error ≤ 0.12 , half width ≤ 0.23). Expanded Sample Size (Anti-Lymphoma Activity): The Cohort B phase 2 portion is expected to enroll and treat a minimum of 19 and a maximum of 35 patients at the Cohort B schedule.

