12.4 Statistical Analysis Plan

In general, data will be summarized by using counts and percents for discrete parameters, and by descriptive statistics (number of observations, mean, standard deviation, median, minimum and maximum) for continuous parameters. Response rates will be calculated as the percent of evaluable patients that have confirmed CR by radiographic response including CT and/or PET scans; 95% Clopper Pearson confidence limits will be calculated for this estimate. Toxicity information recorded will include the type, severity, and the probable association with the study regimen. Tables will be constructed to summarize the observed incidence by severity and type of toxicity. Baseline information (e.g., the extent of prior therapy) and demographic information will be presented as well to describe the patients treated in this study. Time to response and survival endpoints will be estimated using the product-limit method of Kaplan and Meier. The

cumulative incidence of relapse/progression and non-relapse mortality will be calculated as competing risks using the method of Gooley et al¹⁷.

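### The denominator of the reported CR rate is not settled; under the Section 11.1 definition, any treated patient dropped would normally raise the rate above the all-treated rate

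*Combined protocol and SAP*

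**What the plan says.** Section 12.4, and the same sentence in the synopsis under Statistical Considerations, sets the estimate: "Response rates will be calculated as the percent of evaluable patients that have confirmed CR by radiographic response including CT and/or PET scans". A 95% Clopper-Pearson interval goes with it. Neither place says which meaning of evaluable is intended.

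The documents offer several candidates:

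- Section 11.1, for response: participants need measurable disease at baseline, and only those who also "have received at least 4 weeks of therapy, and have had their disease re-evaluated will be considered evaluable for response".
- Synopsis, Sample Size, Cohort A: "43 evaluable (received at least one cycle of treatment) patients will be enrolled on the phase II portion of the study". A nivolumab-only cycle is 14 days (Section 5.1.5).
- Section 12.2: "43 evaluable patients will be enrolled on the phase II portion of the study", with no definition.
- Section 12.1.1, Cohort A Simon rule: "At stage 1, 15 subjects will be entered on the study".
- Section 12.1.1, Cohort B Simon rule: the cohort is "expected to enroll and treat a minimum of 19 and a maximum of 35 patients".

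For toxicity the rule is clear. Section 11.1 states: "All participants will be evaluable for toxicity from the time of their first treatment with nivolumab". No section says how a treated patient without a response assessment enters the CR rate, and no all-treated CR analysis is specified.

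**The concern.** CR rate is the primary endpoint of Cohort A and one of two primary endpoints of Cohort B. The 11.1 definition selects patients on events after treatment starts: staying on therapy for 4 weeks and being re-evaluated. Patients who fail it are mostly those who stopped early, and on the planned schedule they have no documented CR. Leaving them out shrinks the denominator and leaves the numerator alone.

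Two further consequences follow in that case.

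- Cohort B's two primary endpoints would rest on different patients. Someone who stops in week 3 for unacceptable toxicity counts as a toxicity event but disappears from the CR rate.
- The Section 12.1.1 rationale cites one earlier study on an enrolled/treated basis (65%) and another as 34 CRs among 46 accrued. A response-evaluable rate is not like for like with either.

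Because the wording does not choose, the denominator could also be picked after the results are known.

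**Working it through.** **1. The plan's own designs.** The probability of passing at a true CR rate p is the sum over x from r1+1 to n1 of b(x; n1, p) × P[Bin(n − n1, p) > r − x].

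- Cohort A (8/15, 26/43): 0.0499 at p = 0.50 and 0.8044 at p = 0.70.
- Cohort B (9/19, 22/35): 0.0444 at p = 0.50 and 0.9004 at p = 0.74.

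Both match the stated error rates and power. Both treat each of the 43 or 35 patients as either CR or non-CR.

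**2. Who can be dropped.** Measurable disease is an entry criterion (Section 3.1), so that condition removes no eligible patient. The other two conditions can. The first scheduled PET-CT is at the end of week 6 in Cohort A (Section 10.1) and week 8 in Cohort B (Section 10.2). A patient never re-evaluated cannot be a documented CR. A patient with under 4 weeks of therapy stops before the first scheduled scan. Patients with stable or progressive disease at a scheduled scan stay in as non-CR.

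**3. Direction.** With x CRs among n treated and k dropped non-CRs, the shift is x/(n − k) − x/n = xk/[n(n − k)]. This is positive whenever k ≥ 1 and x > 0. The exception is a patient with under 4 weeks of therapy whose CR is documented anyway, for example by an unscheduled early scan. Dropping that patient gives (x − 1)/(n − 1), which is not above x/n.

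**4. Size.** The documents give no number of exclusions, so k = 0, 1 and 2 are assumed. The counts used are the largest failing count (26, 22) and the count nearest the promising rate (30, 26). Rates are in percent, with 95% Clopper-Pearson limits.

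| Cohort, CRs | k = 0 | k = 1 | k = 2 |
|---|---|---|---|
| A, 26 of 43 | 60.5 (44.4–75.0) | 61.9 (45.6–76.4) | 63.4 (46.9–77.9) |
| A, 30 of 43 | 69.8 (53.9–82.8) | 71.4 (55.4–84.3) | 73.2 (57.1–85.8) |
| B, 22 of 35 | 62.9 (44.9–78.5) | 64.7 (46.5–80.3) | 66.7 (48.2–82.0) |
| B, 26 of 35 | 74.3 (56.7–87.5) | 76.5 (58.8–89.3) | 78.8 (61.1–91.0) |

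For k = 1 the shift is x/(43 × 42) in A: 26/1806 = 1.4 points and 30/1806 = 1.7 points. In B it is x/(35 × 34): 22/1190 = 1.8 points and 26/1190 = 2.2 points.

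**5. What Cohort B already shows.** Section 2.5 reports CR in all 13 patients treated so far, and these count toward the 35. Any exclusions would therefore come from the other 35 − 13 = 22. The Cohort B rows above imply 9 of 22 (22 CRs) or 13 of 22 (26 CRs) after 13 of 13. If nearly all respond, one exclusion shifts the rate by at most 34/34 − 34/35 = 2.9 points.

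**6. Replacement.** If a fraction d of treated patients is non-evaluable, all of them non-CR, and each is replaced, the rate among evaluable patients is p/(1 − d). At an all-treated rate of 50% and d = 5%, this is 0.50/0.95 = 0.526. The Cohort A rule then passes with probability 0.095. At d = 2% the figure is 0.065, and at d = 10% it is 0.172. These values of d are assumptions.

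**7. Benchmarks.** 34/46 = 73.9% reproduces the cited 74%; over the 44 transplanted it would be 34/44 = 77.3%. So that figure is on all accrued patients.

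**The case against.** The strongest reply is that only an ambiguity has been shown. The synopsis ties evaluable to one cycle of treatment in the very sentence that sizes Cohort A, and on that reading the denominator is close to all treated. With no exclusions the bias is zero, and the 13 of 13 in Cohort B is reported on a treated basis. One exclusion moves the rate by about 2 points, against intervals roughly 29 to 34 points wide. Much of this stands, and it is why the conclusion is conditional. It does not remove the problem: the one-cycle wording is sample-size text for Cohort A only, and 11.1 is the only definition written for response.

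A reader might infer four stronger things that the documents do not support.

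- *The reported rate will be inflated.* That needs both 11.1 to govern and at least one treated patient to be dropped.
- *The trial decision is compromised.* The Simon rules are counts of CRs. A patient without a documented CR adds nothing to the count, so the decision is the same on a fixed number treated. Only replacement changes that.
- *Every historical comparison is affected.* Denominators are stated for two benchmarks in Section 12.1.1. Those of the Cohort B comparators in Section 2.5 are not stated. It is easy to construct a crossing of the 65% benchmark (27/43 = 62.8%, 27/41 = 65.9%), but no rule tests against 65%.
- *The protocol's delay rule will produce exclusions.* Section 7.2 says "After 14 days of delay, patients must be taken off the trial". In Cohort B, a delayed Cycle 2 (day 15) would reach that point on day 29, and a delayed Cycle 3 (day 36) on day 50, before the scan at day 56. The Section 10.2 calendar marks no imaging at end of treatment. But Sections 7.3 and 7.5 set a limit of more than 6 weeks, with exceptions, and 7.5 keeps tumor assessments going when dosing is interrupted. How these fit together is unstated and must be reconciled, so the route is possible, not established.

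**Conclusion.** The concern holds in conditional form. The denominator of the reported CR rate and its interval is undefined between at least two meanings. If the response-specific one applies and any treated patient without a documented CR is dropped, the reported rate exceeds the all-treated rate. One assumed exclusion is worth 1.4 to 1.7 points in Cohort A (26 to 30 CRs) and 1.8 to 2.2 points in Cohort B (22 to 26 CRs).

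The effect is on the reported estimate, on its comparability with two cited benchmarks, and on consistency between Cohort B's two primary endpoints. The go/no-go decision keeps type I error of 0.0499 (A) and 0.0444 (B) if the counts are applied to a fixed 43 or 35 treated patients without replacement. The Cohort A wording does not rule replacement out; at an assumed 5% non-evaluable it would give 0.095. The Cohort B wording, which speaks of enrolling and treating, does not suggest replacement. This should be fixed before the analysis, but it is not a flaw in the design.

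**What to change.** In Section 12.4, for each cohort:

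- Define the denominator of the reported CR rate and interval as all patients who received at least one dose of nivolumab. Section 11.1 already uses this set for toxicity.
- Count anyone without a documented CR as non-CR.
- State that non-evaluable patients are not replaced for the Simon counts.
- Keep the 11.1 response-evaluable set as a sensitivity analysis, reporting how many patients it excludes and why.

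Align the synopsis (Sample Size and Statistical Considerations) and Sections 11.1 and 12.2 with this. How patients later found ineligible are handled is for the sponsor to choose and state.

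The cost is a few sentences, with no new data or visits. The reported rate may be slightly lower, and a responder who was never scanned would count as non-CR, which can understate the true rate.

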11.2 Transplant Endpoint Definitions

Overall Survival (OS): OS is defined as the duration of time from start of AHCT treatment to time of death (due to any cause). Evaluated and recorded at day 30, day 100, 6 months, 1-year and 2-years post HCT.

Progression-Free Survival (PFS): PFS is defined as the duration of time from start of HCT treatment to time of progression or death, whichever occurs first. Evaluated and recorded at day 30, day 100, 6 months, 1-year and 2-years post HCT.

Relapse/Progression (CIR): The event is relapse/progression. The time to this event is measured from start of HCT treatment. Deaths without relapse/progression are considered a competing risk. Surviving patients with no history of relapse/progression are censored at time of last follow-up. Evaluated and recorded at day 30, day 100, 6 months, 1-year and 2-years post HCT.

Non-relapse mortality (NRM): NRM is defined as death occurring in a patient from causes other than relapse or progression. NRM is measured from start of treatment until non-disease related death, or last follow-up, whichever comes first. Deaths from relapse/progression are considered a competing risk. Evaluated and recorded at day 30, day 100, 6 months, 1-year and 2-years post HCT.

11.2.1 Toxicities and Adverse Events:

The worst grade of all toxicities will be collected from start of conditioning to day -1, and again from day 0 to 30 post-transplant. From day 31 to 100 post-transplant toxicities that are considered serious adverse events will be collected. Toxicity will be assessed and reported using the CTCAE v4.03 scale.

Stem cell mobilization: mobilization regimen used, median number of cells collected, median number of days to reach minimum collection.

Engraftment (Recovery of Granulopoiesis and Megakaryopoiesis): Engraftment will be assessed using two distinct milestones: 1) ANC (neutrophils) $\geq 0.5 \times 10^3/\mu\text{L}$ achieved and sustained for 3 consecutive lab values on different days with no subsequent decline; and 2) Platelets (PLT) $\geq 20 \times 10^3/\mu\text{L}$ independent of platelet transfusion support. For platelet recovery, date should reflect no transfusions in previous 3 days and the first of 3 consecutive lab values on different days.

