- Patients with active autoimmune disease requiring systemic treatments are not allowed. Subjects are permitted to enroll if they have vitiligo, type I diabetes mellitus, residual hypothyroidism due to autoimmune condition only requiring hormone replacement, psoriasis not requiring systemic treatment, or conditions not expected to recur in the absence of an external trigger

| |
|---|
| Investigational Product Dosage and Administration: |
|---|

| |
|---|
| Nivolumab only stage: nivolumab 240 mg IV flat dose every 2 weeks x 6 doses. NIVO + ICE: nivolumab 240 mg IV every 3 weeks x 2 doses. ICE per standard dosing. |
|---|

| |
|---|
| Clinical Observations and Tests to be Performed: |
|---|

| |
|---|
| Physical exams, tumor measurements by radiographic imaging, biopsy of lymphoma, blood tests, and analysis on lymphoma and peripheral blood specimens. See section 10.0 for details. |
|---|

| |
|------------------------------------|
| Statistical Considerations: |
|------------------------------------|

| |
|---|
| Response rates will be calculated as the percent of evaluable patients that have confirmed CR by radiographic response including CT and/or PET scans; 95% Clopper Pearson confidence limits will be calculated for this estimate. Time to response and survival will be estimated using the product-limit method of Kaplan and Meier. Cumulative incidence of relapse/progression will be calculated taking into account incidence of NRM as a competing risk ¹⁷ . Toxicity recording will include the type, severity, and the probable association with the study regimen. Tables will be constructed to summarize the observed incidence by severity and type of toxicity. Baseline information (e.g., the extent of prior therapy) and demographic information will be presented as well, to describe the patients treated in this study. |
|---|

| |
|--|
| In addition to response assessment, using the Lugano criteria, ¹⁶ survival, toxicity information, and lymphoma specimens/plasma samples will be collected for exploratory biomarker evaluation. |
|--|

| |
|--------------------------|
| Sponsor/Licensee: |
|--------------------------|

| |
|--|
| This is a COH investigator-initiated trial with COH holding the IND and BMS providing funding support and drug supply. |
|--|

| |
|--------------------------|
| Case Report Forms |
|--------------------------|

| |
|--------------------|
| Medidata Rave EDC® |
|--------------------|

Table of Contents

| | |
|---|----|

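### Section 11.2 lets NRM include deaths after relapse, so it is not the competing event that CIR and Section 12.4 require; its time origin is also misstated

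*Combined protocol and SAP*

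**What the plan says.** Section 11.2 sets out four transplant endpoints. For CIR, relapse or progression is the event, "The time to this event is measured from start of HCT treatment", and "Deaths without relapse/progression are considered a competing risk".

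NRM follows a different rule. "NRM is defined as death occurring in a patient from causes other than relapse or progression". On timing, "NRM is measured from start of treatment until non-disease related death, or last follow-up, whichever comes first". On competing events, "Deaths from relapse/progression are considered a competing risk". Its landmarks are the same as for the other three endpoints: "Evaluated and recorded at day 30, day 100, 6 months, 1-year and 2-years post HCT".

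The synopsis (Statistical Considerations) states: "Cumulative incidence of relapse/progression will be calculated taking into account incidence of NRM as a competing risk". Section 12.4 goes further and says that the cumulative incidences of relapse/progression and of NRM will both be estimated as competing risks, by a cited method. Section 1.2 lists post-AHCT OS and PFS, CIR and NRM at 100 days, 1 year and 2 years as secondary estimates among transplanted patients. Section 5.5 keeps patients who progress in survival follow-up.

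**The concern.** Two rules sit side by side in Section 11.2. CIR asks which event came first. NRM asks only what the patient died of, whether or not that patient had already relapsed. Splitting all deaths into disease and non-disease deaths is a coherent analysis of overall mortality, but it is not the pair that Section 12.4 analyses. For relapse and NRM to compete, each patient must have at most one of them as a first event.

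The time origin is a second, smaller problem. Transplant OS, PFS and CIR all run from the start of (A)HCT treatment. NRM alone has no such qualifier and uses the phrase by which Section 11.1 starts whole-study OS and PFS.

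At stake is a named secondary estimate. Programmers following Section 11.2 and Section 12.4 could report different NRM figures from the same data. Under the Section 11.2 wording, NRM, CIR and PFS need not add up.

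**Working it through.** The documents give no NRM or CIR figure to reproduce, so the check is on definitions, followed by simple counting.

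**1. Classify every possible history after AHCT.**

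| History | CIR event | NRM event, Section 11.2 wording | NRM event, first-event rule needed by 12.4 |
|---|---|---|---|
| Alive, no relapse | no | no | no |
| Death without relapse | no | yes | yes |
| Relapse, alive | yes | no | no |
| Relapse, then death from disease | yes | no (competing) | no |
| Relapse, then death from another cause | yes | **yes** | no |

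Only the last row differs. Such deaths would be seen, because Section 5.5 continues survival follow-up after progression.

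**2. Size per affected patient.** Post-HCT PFS fails at relapse/progression or death, whichever is first. With complete follow-up and first-event definitions, CIR + NRM + PFS = 1. Each patient in the last row who has died by the landmark adds 1/N to NRM and to the sum. The final N is not given.

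- N = 22 (patients already transplanted after nivolumab alone, Section 2.5): 1/22 = 4.5 percentage points. This is an interim count that can only grow, so 4.5 is a ceiling for Cohort A.
- N = 43 (maximum Cohort A enrolment, all transplanted): 1/43 = 2.3 points.
- N = 43 + 35 = 78 (both cohorts at their maximum, pooled): 1/78 = 1.3 points.

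**3. Illustration (assumed counts, no censoring).** N = 43; 8 relapses, one of these patients later dying of a non-disease cause; 1 death without relapse; 34 alive without relapse.

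- CIR = 8/43 = 18.6%; PFS = 34/43 = 79.1%.
- NRM as worded = 2/43 = 4.7%; sum = 44/43 = 102.3%.
- NRM as first event = 1/43 = 2.3%; sum = 43/43 = 100%.

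In this example, one such patient doubles the reported NRM.

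**4. Origin, read literally.** The shortest planned Cohort A course is 12 weeks (6 + 6 weeks of nivolumab, or 6 weeks of nivolumab then 6 of NIVO + ICE): 12 × 7 = 84 days. Day 30 from first nivolumab would be 84 − 30 = 54 days before salvage ends. Day 100 would be at most 100 − 84 = 16 days after it. For the longest course, 18 × 7 = 126 days, day 100 is 26 days before salvage ends. None of these can be a post-HCT landmark of the same number. Among transplanted patients, the time before AHCT is also immortal, so on this reading early NRM would be biased low.

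**The case against.** The best defence is that Section 12.4 already shows the intent. An analyst who runs relapse and NRM as competing risks would code the relapse-then-other-death patient as CIR only, so the NRM paragraph is a wording mismatch rather than a wrong analysis. The intent is indeed fairly clear. But Section 12.4 does not define NRM, and Section 11.2, where the definition belongs, gives a different event and a different competing event. Following the stated definition gives the wrong quantity.

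Other points stand in part or in full:

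- **CIR is correct as written.** A death after relapse cannot change it. Only NRM, and its agreement with CIR and PFS, is affected. The synopsis sentence concerns CIR alone and carries less weight than Section 12.4.
- **The origin is probably a typing slip.** The section heading, the landmarks and the objective all point to transplant. The day counts above show that the literal reading is untenable; they do not predict a bias.
- **The size is hypothetical.** The documents give no rate of non-disease death after relapse. The exact 1/N excess holds only without censoring, and only at landmarks after the death.
- **The endpoint is minor.** It is descriptive and is listed under the original objectives, not under those of Cohort B.

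**Conclusion.** The concern holds. As worded, NRM in Section 11.2 is not the complement of CIR, and a patient who relapses and later dies of another cause is counted in both, contrary to the competing-risks analysis in Section 12.4. Ignoring censoring, the excess is 2.3 to 4.5 percentage points per such patient on Cohort A numbers, less if cohorts are pooled, and zero if no such patient occurs. NRM is then overstated relative to the first-event definition. The origin error works the other way, but only on a literal reading that the context argues against; it is a correction of text.

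This should be corrected, but its reach is limited to one secondary estimate.

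**What to change.** Rewrite the NRM paragraph in Section 11.2 so that:

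- the event is death without prior relapse or progression;
- time runs from start of HCT treatment, as for CIR;
- relapse or progression is the competing event;
- patients alive without relapse are censored at last follow-up.

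Add a descriptive table of causes of death after relapse, so that non-disease deaths in relapsed patients stay visible. While the paragraph is open, state which date counts as the start of HCT treatment: Section 11.2.1 separates conditioning from day 0, and Section 11.2 does not say which applies.

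The cost is one paragraph and no new data. Relapse dates are already needed for CIR, and Section 5.5 collects progression during follow-up. The event definition would then rest on relapse and death dates, with no judgement of cause of death, which helps because Section 5.5 allows survival data from telephone, email or public records. NRM may come out slightly lower than under the present wording; the deaths that leave it still count in OS. Because Cohort B enrols only after Cohort A is complete, the change would be made to an open-label trial with outcomes already in hand, so the amendment should record its date, reason and expected direction.
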